3.2.2 Secondary Outcome Measures

Secondary outcomes are restricted to:

1) The assessment of the duration of shedding of *Lactobacillus reuteri* (Lr) strain DSM 17938 following administration. This will be determined by an endpoint PCR assay for *L. reuteri* done on stool collected on D3, D5, D12, D15, D18, D24, D28, D36 on all participants.

4 STUDY DESIGN

The study is a single center Phase 1 double blind placebo controlled trial of *Lactobacillus reuteri* DSM 17938 in children aged 2-24 months. The study population is based in a community with a registered clinical trial center in rural Peru where this protocol can be done in a highly controlled setting. The study is intended to enroll healthy children living in a resource constrained setting where chronic undernutrition and diarrheal disease is common, as this is the population that is most likely to receive benefit from the use of this and or other probiotic products for the treatment of acute infectious diarrhea and environmental enteropathy.

Up to 100 subjects will be enrolled in order to obtain the randomization of 60 subjects, who will receive study product or placebo at a ratio of 2:1. Participants will be enrolled between the ages of 8 weeks and 24 months. There will be no age stratification. Participants will be screened with a baseline history and physical examination and laboratory tests to determine the HIV status of the child, as well baseline laboratory tests to evaluate occult infections, hepatic function, and renal function. Upon randomization subjects will be screened and randomized to a treatment arm. Product will be administered under the direct supervision of study staff daily for 5 days. The primary outcome is the safety and tolerability of the product at this dose and formulation. Safety will be assessed by the monitoring of baseline laboratory tests at 5 and 28 days following the initiation of therapy and by AE monitoring. Tolerability will be evaluated by analyzing 28 day diary cards that are distributed to all randomized subjects on which parents record their child's symptoms (specifically fever, anorexia/oral intake, vomiting, diarrhea, irritability, rash, wheezing, or open fields which allows them to describe any issue their child may experience and grade its severity). Secondary outcomes include: 1) The assessment of the duration of shedding of *Lactobacillus reuteri* (Lr) strain DSM 17938 following administration. This will be determined by and endpoint PCR assay for *L. reuteri* done on stool collected on D3, D5, D12, D15, D18, D24, D28, D36 on all participants.

The planned enrollment period is four months and the participation of individual subjects is for 3 months. The study should be completed in 7 months. Safety monitoring by treatment group, i.e., infants assigned to active or placebo study product will be conducted by NIDDK appointed DSMB under the direction of the NIDDK Program

1 **Official.**

2

3

4

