3 group for the last fifteen years. During this time we have had successful recruitment
4 and retention for intensive birth cohort studies and have recruited and trained nurses
5 and health care workers and a study team from the area. The community is
6 experienced in research participation which aids recruitment and retention of study
7 subjects.^{9,36-42}

10 **5.4 Treatment Assignment Procedures**

11 Treatment assignment is based on the order in which subjects complete screening and
12 are assigned a study code. This study code is the same as the treatment vial ID
13 number.

14 **5.4.1 Randomization Procedures**

15 **Randomization.** Upon satisfactory completion of screening, participants will be assigned
16 a study code (different from the PID that accompanied screening data) that is associated
17 with a list completed by the project biostatistician and shared with the individual at
18 BioGaia preparing the treatment vials. This sequential code is associated with treatment
19 vials randomized to one of two treatment groups (T or P) on a 2:1 (T:P) basis with the first
20 randomized subject receiving the first study vial, etc. All vials are identical (see labelling
21 section below) and the Treatment ID on the vial matches the study code number.

22 **5.4.2 Masking Procedures**

23 This is a double masked trial. Only the project biostatistician has the table linking
24 treatment assignment to randomization code. Unmasking of the rest of the study team
25 will occur only when the database is locked for final analysis or if a clinical situation
26 arises in which the PI feels unmasking is necessary for the treatment of a SAE.

27 **5.4.3 Reasons for Withdrawal**

28 A study subject will be discontinued from participation in the study prior to completing 5
29 days of study product administration if:

30 A subject may be discontinued from the study for the following medical or
31 administrative reasons:

- 1 1) Occurrence of an AE, which in the judgment of the investigator suggests an
2 unacceptable risk to the subject to receive a test product (The investigator will
3 follow the subject until satisfactory resolution of the AE or the AE is determined
4 to be stable.) A likely example in this community might be the development of
5 severe falciparum malaria during the product administration period.
- 6 2) Development of ANY condition fulfilling one of the exclusion criteria (except for
7 out of range laboratory values);
- 8 3) Subject/parental request.

9

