11.1 Study Hypotheses and Analysis

A. The primary hypotheses are that *L. reuteri* therapy at the specified dose is safe and well-tolerated in children aged 2-24 months. There are three areas of safety and tolerability that will be assessed in this Phase 1 trial.

- 1. Evidence of bacteremia or invasive infection resulting from the administration of *L. reuteri* 17938.** Baseline and daily temperature measurements will be made during the study period during the product administration phase and then on all scheduled home visits. Complete blood counts with differential counts will be obtained at baseline, on day 5, and on day 28. The evaluation of all documented febrile episodes will include an examination by a physician, and thick smear for malaria, and blood culture for the evaluation of bacteremia if the temperature is greater than 39°C using temporal artery probe measures.

Specific outcome parameters in this category include:

- a. Mean daily temperature
- b. Incidence of fever on study days 1-5
- c. Frequency of temperature readings categorized as fever (adjusted for number of subjects per group)
- d. Number of episodes of *L. reuteri* bacteremia

2. Evidence of toxicity resulting from the *L. reuteri* DSM 17938 preparation.
Participants will have baseline, day 5, and day 28 assessment of hematologic status and

1 renal and hepatic function. Assessment of renal function will include blood urea nitrogen
2 (BUN) and creatinine (Cr). Assessment of hepatotoxicity will include transaminases
3 (AST, ALT) and total bilirubin. Hematologic status will be determined by CBC to
4 measure hemoglobin count and absolute neutrophil count, as mentioned above.

5
6 Specific outcome parameters in this category include:

7
8 a. Mean values for laboratory tests monitored (adjusted for number of subjects per
9 group). These are listed in Appendix D.
10 b. Frequency of out of range values for laboratory tests monitored (adjusted for number
11 of subjects per group). These are listed in Appendix D.

12
13 2. **Clinical tolerance.** The inclusion of a placebo group will allow for comparisons of the
14 prevalence of daily symptom measurements between treatment groups. The
15 symptoms monitored on the daily diary card (fever, anorexia/decreased oral intake,
16 vomiting, diarrhea, irritability, rash, itching, wheezing) are graded by the parent(s) of
17 the participant as mild, moderate, severe, or very severe. Parents report of severity

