16 treatment group. The normal range for each parameter will be used to create categories
17 of low, normal, or high. Any result higher than the upper limit normal (ULN) will be
18 categorized as high, any result lower than the lower limit of normal (LLN) will be
19 categorized as low, and any result within the LLN and ULN will be categorized as normal.
20 The number and percentage of subjects in each shift category from baseline to final
21 evaluation will be shown for each parameter. Only the hematology and blood chemistry
22 tests with a numeric normal range and at least one follow-up value will be analyzed for
23 shifts from baseline. The number and percentage of subjects with clinically significant
24 values will be presented.

25
26 **B. The secondary outcome measurements** are

27
28 1. To determine the duration of shedding of *L. reuteri* DSM 17938 following controlled
29 administration.

30
31 Since the longitudinal nature of the repeated PCR assays results in correlated outcomes,
32 generalized estimating equations (GEE) will be used to model the binary response
33 whether subjects exhibited a positive PCR result during the various period of study. The
34 duration of shedding of *L. reuteri* will be assessed using Kaplan Meier Product limit
35 estimates.

36
37
38
39
40 **11.2 Sample Size Considerations**

1
2
3 The sample size for this Phase 1 safety trial in healthy children aged 2-24 months is
4 determined by historical precedent for safety in human use.

5
6 Enrollment for the prior Phase 1 studies in adults (Safety of LR in Healthy volunteers
7 #NCT00774163) and children (Safety of LR in healthy children 2 to 5 years of age in Peru
8 #NCT02124122) have been able to recruit and retain >95 subject (Phase 1 child study in
9 progress). We have high and similar rates of retention in our other studies with more
10 complexity and participant burden, even among our birth cohorts.³⁷

11
12 Missing data will not be imputed. Data will be analyzed per treatment group assignment
13 after the administration of a single dose of product for all safety and tolerability analyses.
14 Data regarding the duration of carriage will be restricted to those individuals who complete
15 5 days of therapy.

16
17 The amount of subjects in this study will likely be underpowered to detect differences in
18 most secondary outcomes. This is in part due to the lack of information on key

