APPENDIX D: LABORATORY VALUES*

Serum Chemistries (normal range for 0-2 year old children at our reference lab)	Mild (Grade 1)	Moderate (Grade 2)	Severe (Grade 3)	Potentially Life Threatening (Grade 4)**
8. Bilirubin, mg/dL (\leq 1.0)	1.1-1.9	2.0-2.9	3.0-7.5	>7.5
9. Blood Urea Nitrogen BUN mg/dL (\leq 23)	24-60	61-80	\geq 81	Requires dialysis
10. Creatinine, mg/dL (\leq 0.4)	0.5 – 1.0	1.1 – 1.6	1.7 – 2.0	> 2.0 or requires dialysis
11. Liver Function Tests –ALT (\leq 52) units per liter (U/L)	53-200	201-400	401-600	> 600
12. Liver Function Tests –AST (\leq 39) units per liter (U/L)	40-200	201-400	401-600	> 600

Hematology	Mild (Grade 1)	Moderate (Grade 2)	Severe (Grade 3)	Potentially Life Threatening (Grade 4)
13. Children 6-24m : Hemoglobin gm/dL (\geq 11)	10.0 – 10.9	7.0 – 9.9	< 7.0	Cardiac insufficiency due to anemia
13a. Children 2-5 m: Hemoglobin gm/dL (\geq 9.5)	9.4-8.5	6.5-8.4	<6.5	Cardiac insufficiency due to anemia
14. Total WBC Count - cell/mm ³ (6,000-17,500)	17,501 – 20,000	20,001 – 25,000	25,001 – 28, 000	> 28,000

* Based on NIAID Division of AIDS Table for Grading the Severity of Adult and Pediatric Adverse Events, December 2004
(<http://www.niaid.nih.gov/labsandresources/resources/daidsclinrsrch/documents/daidsaegradingtable.pdf>), adapted for normal reference values for age for our reference laboratory (Asociacion Civil Selva Amazonica: Iquitos, Peru; www.selvaamazonica.org)

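### Safety is claimed for ages 2-24 months, but non-serious AEs, symptoms, fever and laboratory means are reported only overall and by arm, with no age-band display or age adjustment

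*Combined protocol and SAP*

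**What the plan says.** - **Population.** Section 4: "Participants will be enrolled between the ages of 8 weeks and 24 months". The same section adds: "There will be no age stratification".
- **Claim.** The primary hypotheses in section 11.1 are that *L. reuteri* "therapy at the specified dose is safe and well-tolerated in children aged 2-24 months", with the age range treated as one group.
- **Size and allocation.** Section 4: "Up to 100 subjects will be enrolled in order to obtain the randomization of 60 subjects", at 2:1, so 40 active and 20 placebo. Section 11.2 says the size is "determined by historical precedent for safety in human use". Section 5.4.1 describes one sequential list with no stratum.
- **Analysis.** Section 3.2.1 says outcomes will be compared between the two arms. Section 11.1 summarises laboratory values, changes from baseline and shifts for all subjects and by arm. The only adjustment attached to the primary outcomes is for arm size, which is a denominator. The one covariate the plan says it will control for is iron supplementation (section 7.5). No age band or age covariate appears in the planned analysis.
- **Where age does enter.** Appendix D has a separate row, "13a. Children 2-5 m: Hemoglobin gm/dL", with a normal limit of 9.5 g/dL, against 11 g/dL at 6-24 months. Section 7.5 applies a different hemoglobin threshold at 5 months or younger. Chemistry and white cell count have one range for all ages.

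**The concern.** The claim is broader than anything the analysis will display. It reaches down to 8 weeks of age, while this programme's own earlier Phase 1 trials covered adults and children of 2-5 years. If most enrolled children are older, pooled AE and symptom percentages mainly describe them. An excess of fever, vomiting or irritability confined to young infants could then appear as a small overall difference. A reader would not know how many 2-5 month infants received active product, or what was seen in them.

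A second, smaller issue is that with 20 placebo children the arms may differ in age by chance. The plan has no rule for reading between-arm differences in laboratory means or symptoms when that happens.

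**Working it through.** **The plan's own figure.** 60 at 2:1 gives 60 × 2/3 = 40 active and 60 × 1/3 = 20 placebo. The 60 itself cannot be recomputed, because section 11.2 gives no alpha, power, event rate or margin.

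**How many young infants (assumption: entry age uniform from 8 weeks to 24 months).** 8 weeks is 56/30.4375 = 1.84 months. The share under 6 months is (6 − 1.84)/(24 − 1.84) = 18.8%. That is about 11 of 60, or 7 to 8 of 40 active (0.188 × 40 = 7.5), taken below as 7 active and 4 placebo.

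**What zero events would show.** The exact two-sided 95% upper limit for 0/n is 1 − 0.025^(1/n).

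| Active infants, no events | Upper limit |
|---|---|
| 40 (all ages) | 8.8% |
| 12 (share 30%) | 26% |
| 7 (uniform age) | 41% |
| 4 (share 10%) | 60% |

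**Dilution (assumed rates).** Suppose a non-serious AE has a 10% background rate and a 40% rate in the 7 youngest active infants only. The pooled active rate is (7 × 0.40 + 33 × 0.10)/40 = 6.1/40 = 15.3%, against 10% on placebo. The power to see that difference is about 7% by normal approximation and 4% by Fisher's exact test (simulated). A Fisher test within the youngest band alone has about 1%. With 20% and 60% instead, the pooled rate is (7 × 0.60 + 33 × 0.20)/40 = 27% against 20%. Fisher power is then about 6% pooled and 7.5% in the band. So the pooled comparison does not show the effect, and a subgroup test would not rescue it.

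**Chance age imbalance.** With 11 of 60 children under 6 months, let X be the number on placebo; X is hypergeometric (60, 11, 20). The difference in shares is (11 − X)/40 − X/20.
- It is at least 20 points in size when X ≤ 1 (probability 5.6%) or X ≥ 7 (2.5%), in total 8.1%.
- With 6 such infants in the trial the figure is 1.3%; with 20 it is 15.4%.
- X = 1 gives exactly 20 points, so strictly more than 20 points happens 3.1% of the time.

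If typical hemoglobin differed between the bands by the gap between their limits (11 − 9.5 = 1.5 g/dL, an assumption), a 20-point imbalance would shift the raw difference between arm means by 1.5 × 0.20 = 0.3 g/dL.

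**The case against.** Several stronger readings are tempting, and the documents do not support them.

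- **That pooling could hide serious harm.** Section 9.2.2 makes *L. reuteri* bacteremia and every Grade 3 or 4 monitored laboratory value an SAE. Section 11.1 lists all SAEs and all AEs leading to withdrawal. Section 9.5 halts the study on two similar SAEs whose relation to product cannot be excluded, at any age. What remains is non-serious AEs, symptoms, fever and laboratory means.
- **That the plan ignores age.** Hemoglobin grading is age-banded. Changes from baseline are summarised, which removes much of any age-related difference in laboratory level. Out-of-range baseline chemistry or white cell count excludes a child. None of this touches age-related AE or symptom risk, and raw laboratory means remain a named outcome.
- **That young infants are untested.** Section 2.3.1 cites earlier studies of this product in low birth weight newborns and in infants with colic. They bear on prior plausibility. They do not replace reporting what this trial observed.
- **That unstratified randomisation is a fault or biases the comparison.** It is a legitimate choice at N = 60. Chance imbalance is imprecision, not bias.
- **That imbalance is common.** A 12-month cut (28 of 60 if age is uniform) gives at least a 20-point difference 18% of the time, but that cut is nowhere in the plan. Strictly above 20 points, it falls to 10%.

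Two further objections stand. The number of young infants is inferred, since no age distribution is given. The band is also too small for inference. The Data and Safety Monitoring Plan is a separate document not seen here and may contain further tables.

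**Conclusion.** The point holds in a limited form. The hypothesis covers 2-24 months, and the analysis described in the protocol would display no number specific to the youngest infants for non-serious AEs, symptoms, fever or laboratory means. It also has no age adjustment.

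Under uniform entry age, no events in about 7 active infants under 6 months would be compatible with a true rate of up to 41%. The pooled 0/40 figure would suggest 8.8%. For 4 to 12 such infants the limit runs from 60% to 26%. The dilution figures rest on assumed event rates and illustrate the mechanism; they are not forecasts. The imbalance risk is modest, about 8% at the protocol's own age cut and sensitive to the number of young infants. The trial remains sound as designed. What needs to change is the display and how far the conclusion reaches.

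**What to change.** Keep unstratified randomisation. In section 11.1:

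1. Add a descriptive table of AEs, fever and laboratory outcomes by arm within the 2-5 and 6-24 month bands of Appendix D, giving the number exposed and exact 95% intervals. Plan no subgroup test.
2. Adjust between-arm comparisons of day 5 and day 28 laboratory means for baseline value and age at entry. This addresses chance imbalance directly. Stratum-combined symptom estimates would add little with about 7 versus 4 infants in one band.
3. State the number of active infants aged 2-5 months beside any safety conclusion.

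The cost is a few extra tables and one adjusted model per laboratory outcome, all from data already collected. The downside is wide intervals in the younger band, which reflect how little this trial can say about that group.

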5 STUDY ENROLLMENT AND WITHDRAWAL

1

2 **5.1 Subject Inclusion Criteria**

3

4

5 In order to be eligible to participate in this study, a subject must meet all of the following
6 criteria:

7

- 8 • Have a parental permission form signed by both parents
- 9 • Be between 8 weeks to 24 months of age with no preexisting exclusion criteria
- 10 • Have parents who are willing to comply with all planned study procedures and be available for planned study visits for 3 months.

1
2 **5.2 Subject Exclusion Criteria**

3
4 1) No enrollment of family members in households where any of the following are
5 present:
6
7 a. Another study participant in the household
8
9 b. Presence of immune suppressed individuals or use of immunosuppressive
10 agents (including but not limited to corticosteroids, methotrexate, etc.) by any
11 household member
12
13 c. Presence of a serious congenital anomaly or chronic medical condition that in
14 the opinion of the investigators would contraindicate participation in any household
15 member, including history of gastrointestinal surgery, chronic gastrointestinal
16 illness, abnormal intestinal anatomy, or abnormal bowel functionality
17

18 The following risk factors are at the level of the individual child:

19
20 2) Allergy to penicillin, cephalosporins, clindamycin or gentamicin
21 3) History of antibiotic use in the last 30 days
22 4) Use of probiotic products within the past 30 days, including masato (local
23 product with fermenting bacteria) and yogurt products containing live
24 bacterial cultures.
25 5) History of diarrheal illness within the past 30 days (See definition in Protocol
26 Appendix B)
27 6) Presence of fever or a pre-existing adverse event monitored in the study
28 (See Protocol Appendix B Definitions of AEs for specific adverse events
29 monitored in the study)
30 7) Positive results on serum diagnostic tests for antibodies to HIV.
31
32 8) Presence of severe anemia, defined as serum hemoglobin \leq 7 gm/dL
33
34 9) Out of range laboratory values for total leucocyte count, BUN, Creatinine,
35 AST, ALT, and total bilirubin monitored as potential adverse events, as
36 described in Appendix E.
37 10) Pre-enrollment stool sample (collected within 14 days of day 1 of the study)
38 is positive for *L. reuteri* by PCR.
39
40

1 **5.3 Strategies for Recruitment and Retention**

2 The community where recruitment will occur has been a research site for the current
3 group for the last fifteen years. During this time we have had successful recruitment
4 and retention for intensive birth cohort studies and have recruited and trained nurses
5 and health care workers and a study team from the area. The community is
6 experienced in research participation which aids recruitment and retention of study
7 subjects.^{9,36-42}

10 **5.4 Treatment Assignment Procedures**

11 Treatment assignment is based on the order in which subjects complete screening and
12 are assigned a study code. This study code is the same as the treatment vial ID
13 number.

14 **5.4.1 Randomization Procedures**

15 **Randomization.** Upon satisfactory completion of screening, participants will be assigned
16 a study code (different from the PID that accompanied screening data) that is associated
17 with a list completed by the project biostatistician and shared with the individual at
18 BioGaia preparing the treatment vials. This sequential code is associated with treatment
19 vials randomized to one of two treatment groups (T or P) on a 2:1 (T:P) basis with the first
20 randomized subject receiving the first study vial, etc. All vials are identical (see labelling
21 section below) and the Treatment ID on the vial matches the study code number.

22 **5.4.2 Masking Procedures**

23 This is a double masked trial. Only the project biostatistician has the table linking
24 treatment assignment to randomization code. Unmasking of the rest of the study team
25 will occur only when the database is locked for final analysis or if a clinical situation
26 arises in which the PI feels unmasking is necessary for the treatment of a SAE.

27 **5.4.3 Reasons for Withdrawal**

28 A study subject will be discontinued from participation in the study prior to completing 5
29 days of study product administration if:

30 A subject may be discontinued from the study for the following medical or
31 administrative reasons:

- 1 1) Occurrence of an AE, which in the judgment of the investigator suggests an
2 unacceptable risk to the subject to receive a test product (The investigator will
3 follow the subject until satisfactory resolution of the AE or the AE is determined
4 to be stable.) A likely example in this community might be the development of
5 severe falciparum malaria during the product administration period.
- 6 2) Development of ANY condition fulfilling one of the exclusion criteria (except for
7 out of range laboratory values);
- 8 3) Subject/parental request.

9

10

11 **5.4.4 Handling of Withdrawals**

12

13

14 The study is voluntary and allows for the withdrawal of participation at any point in the
15 study. Despite this, we have a very low attrition rate in our studies. In general
16 withdrawal from the study is partial- most frequently related to blood draws. In all
17 cases, the reason for the withdrawal of consent will be discussed at length with
18 parents. We will ask that the parents of the participant to continue to allow visits to
19 monitor vital signs and illness history at the least. In most cases our experience
20 informs us that parents will allow stool collection to continue. Blood draws are the most
21 problematic- we will allow the family to opt for a fingerstick sample if the venous blood
22 draw experience is that which is underlying the withdrawal. We also would allow for
23 extended windows (i.e., blood draw at 35 days rather than 28 if the parent feels more
24 time between blood draws would allow for their continued complete monitoring,
25 although in this case a protocol deviation form would be included with the values. In
26 short, every attempt will be made to obtain the most complete safety and tolerability
27 data possible while respecting parental autonomy and their right to cease participation
28 in a voluntary study. No replacement of subjects is planned, and we expect the
29 number of consent withdrawals and missed study visits or missed study procedures to
30 be low.

31

32 **5.4.5 Termination of Study**

33

34

35 This study may be prematurely terminated if, in the opinion of the PI or sponsor there is
36 sufficient reasonable cause for termination. An example of a reason underlying
37 termination would be NIDDK concurrence with DSMB recommendation to end study
38 early, new findings that alter the safety profile of the product, discontinuation of study
39 product for active and matching placebo production or impending market
40 unavailability, the discovery of important protocol violations that may undermine the
41 integrity and conclusions of the study.

42 If the study is prematurely terminated or suspended, the sponsor will promptly inform

1 the investigators/institutions so that the investigators can inform the U.S. and Peruvian
2 regulatory authority(ies) of the termination or suspension and communicate the
3 reason(s) for the termination or suspension. The IRB/IEC will also be informed
4 promptly and provided the reason(s) for the termination or suspension by the sponsor
5 or by the investigator/institution.
6

